Ionizing radiation causes tissue damage by releasing free radicals leading to oxidative stress [13]. The ionizing irradiation of water molecules in the cells leads to aqueous radiolysis, creating free radicals [14]. These free radicals may react with macromolecules, such as DNA, RNA, proteins, and cell membranes, eventually leading to dysfunction of cells and cell death [13].

The sleep-hormone melatonin reduces oxidative stress [15, 16]. Melatonin is amphiphilic and distributes freely between all body compartments [17-19]. Studies have documented that melatonin is a strong free radical scavenger. The anti-oxidative effects of melatonin may therefore provide protective effects against the damage of ionizing radiation in clinical cancer treatment and radiological imaging procedures [20]. In animal studies, melatonin protects the healthy tissue against radiation injury [20]. However, melatonin has also been documented to possess oncostatic and pro-apoptotic effects in cancers in experimental studies [21, 22], and has been demonstrated to sensitize human breast cancer cells to ionizing radiation in cell culture studies [23, 24].

A report describing the expected incidence of cancers up until 2020, predicts a yearly incidence of approximately 4800 cases of breast cancer in Denmark alone [25]. These numbers suggest that if melatonin can protect against radiation injury, a large number of patients could be candidates for melatonin treatment, and thereby obtain a better quality of life. A previous study

demonstrated the radioprotective effect of melatonin in the treatment of breast cancer [11]. This study included patients receiving breast-conserving surgery, and randomized them to receive either melatonin or placebo in a cream, which was applied twice daily. This study demonstrated a protective effect of melatonin against radiation dermatitis in women receiving 50 Gy of radiation [11]. However, this study did not list the dose of melatonin applied, and only used the RTOG scale as an outcome parameter. No subjective outcomes were measured in this study [11]. The authors of the previous study have not been able to inform us of the dose of melatonin used in the study (personal communication).

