Melatonin has the disadvantage of being unstable when exposed to air and light. A study demonstrated that melatonin in aqueous solutions at room temperature, and at neutral pH, degrades by 29% over 21 days [26]. The compound dimethyl sulfoxide (DMSO) has seen wide use both as a solvent and as an anti-inflammatory drug [27, 28]. Based on a report made available to the authors from the pharmaceutical company, Bioneer A/S, melatonin dissolved in DMSO undergoes no degradation over 45 days when stored at 25 °C temperature, away from light.

The aim of the present randomized double-blinded placebo-controlled clinical trial is to investigate if melatonin can protect against acute radiation dermatitis in patients with early breast cancer receiving radiation therapy, and whether this has an impact on the patients' quality of life.

Study design

The study is registered at clinicaltrials.gov (indsæt ID, når dette er sket). This is protocol version 1.0, 13/09/2018. The study will be a randomized, placebo-controlled, double-blinded clinical pivotal trial. Patients will be allocated in a ratio of 1:1 to the melatonin or placebo group. Patients will be stratified according to the type of surgery (lumpectomy or mastectomy). Randomization will be performed in blocks of randomized sizes. The study will be performed in the Department of

Oncology, Rigshospitalet, Denmark. Patients will be included into our study according to specific eligibility criteria (see Table 1).

Interventions

Eligible patients with early breast cancer receive adjuvant radiation therapy over 15 to 30 daily fractions (5 fractions per week) of ionizing megavoltage photon radiation to a total of 40 - 60 Gy within 3-5 weeks according to the guidelines of the Danish Breast Cancer Cooperative Group [29].

In our study, the patients will administer approximately 1 g of cream containing melatonin (25 mg/g) and dimethyl sulfoxide (DMSO) (150 mg/g) or a placebo cream topically twice daily on the irradiated skin area. They are scheduled to do this every day from the first to the last fraction of radiation therapy, including the days where they do not receive radiation therapy. We have chosen placebo as our comparator due to it being safe, and in our view the most reasonable method of evaluating any effects of the intervention. On days where the patients receive radiation, the melatonin/DMSO or placebo cream will be applied no less than 2 hours prior to radiation.

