Patients will be randomly assigned to either a control or experimental group allocated in the ratio of 1:1 by use of a computer-generated randomization schedule. Patients will be stratified according to whether they have undergone lumpectomy or mastectomy. We will randomize the block size to between 4 and 8 patients per block. Each block will therefore consist of patients who have undergone either lumpectomy or mastectomy, allocated in a 1:1 ratio. Block size will be concealed to the investigators until the end of the trial (i.e. after data analysis and statistical evaluation). The allocation sequence will be generated by a staff member with no other involvement in the trial. Assignments will be placed in sequentially numbered, opaque, sealed envelopes with the randomization number printed on them. These envelopes will be packed by a staff member with no other involvement in the trial. Every assignment will contain a code that corresponds to tubes of the melatonin/DMSO or placebo preparation. The primary investigator will enroll and assign participants to intervention on the basis of the assignment code from the envelope. Envelopes as well as tubes with active and placebo cream will be stored in a locked cabinet at Rigshospitalet.

Outcome assessment will be performed by the primary investigator, who is blinded to treatment allocation. Participants are also blinded to treatment allocation. The primary investigator will be blinded when performing data analysis and statistical evaluations.

Should the investigator deem it necessary for the safety of the patient, the investigator can un-blind a patient. Treatment-allocation will be noted in a document on a secure folder on a drive on the server of the Region Hovedstaden. Should an investigator need to un-blind a patient, they can access this document from their computer. Treatment allocation will only be un-blinded if it is imperative to the treatment of the patient. The treatment allocation will in this case only be

revealed to one other investigator than the primary investigator. This investigator will oversee the treatment of the patient. Registration of adverse reactions is described in the “Harms” section.

Drop-outs and patient retention

We plan to promote participant retention and complete follow up by asking for contact information (phone number and e-mail) and preferred way of contact. We will schedule appointments with patients at same location, accommodating their calendar, as far as possible.

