distributed data will be analyzed with non-parametric tests (e.g. Mann-Whitney U test). Our primary outcomes are the RTOG scores and the image analysis two weeks after the last radiation fraction, as well as the QLQ-BR3 breast symptoms on the last day of radiation therapy. Our secondary outcomes will be analyzed as follows: We will analyze steroid usage through two different outcomes. Days of steroid usage will be analyzed through either parametric or non-parametric tests. Any steroid usage (yes/no) will be analyzed through χ^2 or Fisher's Exact test. The RTOG scores, the quality of life questionnaires, and the image analysis values for the entire period will be analyzed in a mixed linear model, which takes correlation between patients into account. Subgroup analyses will be performed for mastectomized and lumpectomized patients respectively, if feasible. Other subgroup analyses may be performed based on background variables (fractionation schedule, histopathology and demographic data). Missing data will be taken into consideration when using the mixed linear model. A detailed statistical analysis plan will be formulated and be supervised by a bio-statistician prior to study start.

Data management

All outcomes will be collected by the primary investigator at time points listed in table 3. All data entered into the electronic case report form (eCRF) will be validated through “required fields” and format (e.g. date-format) where applicable. In the clinical photographs, patients will be marked with patient-ID written on tape, fixed to the patients’ chest. The time-stamp of the photograph will be noted in the eCRF. a*-values will be imported into the eCRF.

Our data will be stored electronically in Research Electronic Data Capture (REDCap), an electronic database used throughout the Capital Region of Denmark. All confidential data will be stored in a secure server for 15 years after patient enrollment in the study. Only the investigators and the Good Clinical Practice (GCP) Unit will have access to these data. After conclusion of the study, a final anonymized dataset will be available to RepoCeuticals ApS who has sponsored the

study through a grant through a formalized research contract between the Capital Region of Denmark and the company. Ownership of data is shared between the investigators and RepoCeuticals ApS.

Monitoring

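### The primary comparisons are planned as unadjusted two-sample tests that ignore both the surgery stratum and the recorded radiation schedule, which costs precision but does not bias the trial

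*Combined protocol and SAP*

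**What the plan says.** **Randomisation.** Surgery type is the only stratification factor. The Study design section states it, and Randomization and blinding repeats it: "Patients will be stratified according to whether they have undergone lumpectomy or mastectomy". Allocation is 1:1 in blocks of random size between 4 and 8 within each surgery group.

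**Radiation.** The Interventions section describes courses of 15 to 30 daily fractions, five per week, "of ionizing megavoltage photon radiation to a total of 40 - 60 Gy within 3-5 weeks". Table 1 does not restrict eligibility to one schedule; bolus use is the only exclusion that concerns radiation technique. Table 2 lists dose and fractionation as background variables taken from the treatment plan.

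**Analysis.** For the between-arm comparisons, Statistical analyses names parametric or non-parametric two-sample tests according to how normal the data look, with the unpaired t-test and the Mann-Whitney test as examples. The primary time points are two weeks after the last fraction (RTOG, image analysis) and the last day of radiation (breast symptoms). No covariate is named for these tests or for the mixed model over the whole period. Surgery type reappears only as a subgroup analysis, if feasible. Schedule reappears only in this sentence: "Other subgroup analyses may be performed based on background variables (fractionation schedule, histopathology and demographic data". A detailed analysis plan is promised before study start but is not among the documents.

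**The concern.** Two pieces of baseline information are available and unused in the primary tests.

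- **Surgery type.** Stratified randomisation balances the arms on it. If it predicts outcome, the real sampling error of the treatment difference is smaller, but an unadjusted test still counts the between-stratum variation as noise and so gives up precision.
- **Radiation schedule.** Radiation causes the condition being measured, and schedule also sets how long the cream is used, since application runs from the first to the last fraction. It is therefore a likely prognostic variable, and neither the design nor the analysis accounts for it.

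At stake are power and how a single result is read. The breast-symptom calculation, which sets the sample size, has no slack. With 24 to 40 patients per arm, a visible difference in schedule mix could leave readers unsure how much of the result is due to the cream.

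**Working it through.** **Inputs from the protocol (Sample size calculations).** Breast-symptom mean 82.2, SD 15.1, target 70, so the difference is 12.2. Alpha 5% (taken as two-sided), power 80%, 24 per arm; about 80 patients included, so at most 40 per arm.

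**Assumed, because the documents give no figures.** Share of patients on the minority schedule: 10-50%. Difference between schedules on breast symptoms: 0-15 points.

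**1. The plan's own figure.** n per arm = 2(1.96 + 0.8416)² × 15.1² / 12.2² = 2 × 7.849 × 228.01 / 148.84 = 24.05. The stated 24 reproduces to rounding. Power at 24 per arm is 79.9% by the normal approximation and 78.2% for the t-test.

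**2. How often the arms differ in schedule.** The SD of the difference in shares is √(2p(1−p)/n); for p = 0.5 and n = 24 it is 0.144. The table gives the exact probability, from two independent binomials, that the shares differ by 20 points or more. That means at least 5 patients at 24 per arm (5/24 = 20.8%) and 8 patients at 40 per arm.

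| Minority share | 24 per arm | 40 per arm |
|---|---|---|
| 10% | 3.0% | 0.5% |
| 20% | 10.3% | 3.5% |
| 30% | 15.5% | 6.7% |
| 50% | 19.3% | 9.3% |

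**3. What a 20-point imbalance does to one unadjusted result.** Shift = 0.20 × gap. Standard error = 15.1 × √(2/24) = 4.36. Power = Φ((12.2 − shift)/4.36 − 1.96) when the imbalance goes against the drug.

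| Gap (points) | Shift | Share of 12.2 | Power | Error rate given this imbalance, no drug effect |
|---|---|---|---|---|
| 5 | 1 | 8% | 73% | 5.6% |
| 10 | 2 | 16% | 65% | 7.4% |
| 15 | 3 | 25% | 56% | 10.6% |

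The last column is conditional on the imbalance having occurred. Averaged over all randomisations, the unadjusted test kept its level: 4.5-5.5% in simulation.

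**4. What adjustment recovers.** If the total SD is 15.1, the SD left after removing schedule is √(15.1² − gap² × p(1−p)). For p = 0.5 and a 10-point gap this is √(228.01 − 25) = 14.25; for 15 points it is √(228.01 − 56.25) = 13.11. Simulated power at 24 per arm (blocked randomisation within surgery strata, 70% lumpectomy assumed, schedule independent of surgery, schedule as the covariate):

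| Minority share | Unadjusted | Adjusted, 5-point gap | 10-point gap | 15-point gap |
|---|---|---|---|---|
| 20% | about 78% | 78% | 79% | 84% |
| 30% | about 78% | 77% | 81% | 86% |
| 50% | about 78% | 78% | 82% | 89% |

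These rest on 4,000 runs per cell. A rerun with 20,000 gave 87% in the bottom-right cell, so read the top of the range as 87-89%. In the same rerun, adjusting for a schedule with no effect cost about one point of power, and a 10% minority share gained three points or less.

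**The case against.** **The main objection is right on bias.** Randomisation leaves chance imbalance in every unstratified factor, and the standard error already allows for it. The 1-3 point shifts above are 0.23 to 0.69 of one standard error (1/4.36 to 3/4.36). The cost is in precision and interpretation only.

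**The sizes rest on assumptions.** The schedule mix, the gap and the 20-point threshold are not in the documents, and a 50% share gives the largest imbalance. If schedule follows surgery type, the surgery strata already balance part of it. This stands, and is why ranges are shown.

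**The promised analysis plan may already adjust.** It may, and the tests are given only as examples. The present text does not commit to adjustment, however.

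**Why schedule rather than skin type, breast volume or chemotherapy?** This is partly fair. Surgery type belongs in the model because the randomisation uses it. Schedule has the next best claim because it defines the exposure and the length of cream use. With 48 patients the list should stay short.

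**A reader might infer more: that randomisation must also be stratified by schedule.** The documents do not support that.

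- Nothing says the schedule is final when the envelope is opened. Table 3 only places randomisation at a baseline visit before the first fraction.
- The text gives a range of fractions and no natural cut-point.
- Four lists instead of two, with blocks of up to 8, would double the worst-case part-block imbalance from 2 × 4 = 8 to 4 × 4 = 16 patients.

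**Nor do they show that imbalance would move all three primary outcomes the same way.** If the ends of the ranges go together, 40/15 = 2.67 Gy per fraction and 60/30 = 2.0. Total dose and dose per fraction then run in opposite directions, so a 50% higher total does not show which schedule is harder on skin. Fractionation subgroups are only something that may be done. That the RTOG planning rates come from women given 50 Gy is a matter for those rates; neither stratification nor adjustment addresses it.

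**Conclusion.** The point holds as a loss of precision that can be avoided at almost no cost. As written, the primary tests ignore the factor used to stratify the randomisation and a recorded baseline variable that is likely to matter. It does not show bias or an inflated overall error rate, and it does not make the randomisation scheme defective.

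A schedule imbalance of 20 points or more has a probability of about 3-19% at the planned 24 per arm, and 0.5-9% if 40 per arm are evaluable. The power gain at 24 per arm depends on the assumed gap between schedules: essentially none at 0-5 points, and from about 78% to 81-89% at 10-15 points with 30-50% on the minority schedule (79-84% with 20%). The gain from including surgery type cannot be sized, because the documents give no outcome difference by surgery. This is an improvement worth making before start, not a condition for the trial to be valid.

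**What to change.** Keep the randomisation as it is. In the detailed analysis plan, before unblinding:

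- **Name two covariates for all primary analyses:** surgery type and planned radiation schedule. Use the schedule in the treatment plan, not what was delivered, so that it remains a baseline value, and fix its coding in advance.
- **Name the models:** for example, linear regression for the a*-value and breast symptoms, and ordinal or logistic regression, or a stratified rank test, for RTOG.
- **Put the same two covariates in the mixed model.**
- **Keep the unadjusted tests as a sensitivity analysis,** so that the result remains comparable with the sample size calculation.

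To code schedule, one discrepancy needs reconciling: 30 fractions at five per week take 30/5 = 6 weeks, while Interventions gives 3-5 weeks and Table 3 has five weekly treatment visits.

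The cost is a few lines of text. No new data, patients or envelopes are needed, and if schedule turns out not to matter the loss is about one point of power. Adding schedule as a stratification factor remains open to the sponsor if the schedule is known at randomisation, but it is not required.

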If a patient does not wish to complete all three follow-up visits, some of the outcomes can be filled in electronically from home, should the patients wish to do so. These outcomes are the QLQ-C30 and QLQ-BR23 questionnaires, and steroid usage outcomes. All data from drop-outs will be used in statistical analyses. Discontinuation of treatment will only occur in the following eventualities: the patient withdraws consent, or if the sponsor decides to terminate the study due to serious adverse events.

Conclusion of study

Recruitment of patients will be concluded when 48 patients have completed the study (see sample size calculations below, in the “Statistics” section). The study will be concluded, when all patients included have completed the study.

Handling of drugs

Storage

The active cream will consist of 25 mg/g melatonin as well as 150 mg/g DMSO, in a cream base. The placebo will consist of just the cream base. The cream base consists of polysorbate 80 (0,5%), cetostearyl alcohol (5%), paraffin oil (5%), glycerol monostearate 40-50 (6%), methyl

parahydroxybenzoate (0,1%), glycerol 85% (4%), sorbitol (7%), purified water (72,4%). The dose for each application will be 1 g, and the cream will be packaged in 30 g tubes. The tubes will be stored at room temperature, in a locked cabinet, in the office of one of the investigators. The cream will be produced and packaged by Glostrup Apotek in their manufacturing facility, according to EU GMP-guidelines. The tubes will be labelled with all required information listed in the EU GMP-guidelines concerning investigational medical products. All drugs will be delivered directly to the sponsor, who will document receiving the products according to GCP-guidelines (modtagekontrol).

Patients will be given one tube of cream at a time, and a second and third tube will be given to them, once the previous tube is empty or running low. Patients will be instructed to keep the tubes out of reach of children, away from sunlight and at room temperature. These instructions will also be listed on the label of the cream.

Administration

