The sample size calculation for the RTOG acute radiation morbidity scoring criteria is based on the findings in a previous study examining melatonin as a radiation protector of the skin in patients receiving radiation therapy for breast cancer [11]. In this study, at two weeks follow-up, 41% of the patients receiving melatonin had toxicity grade 1-2 vs 90% of the patients receiving placebo.

Incidence in placebo group: 90%

Incidence in melatonin group: 41%

Alpha: 5%

Beta: 20%

Sample size needed: Two groups of 14 patients, totaling 28 patients.

The sample size calculation for the image analysis is based on the study evaluating erythema after exposure to ultraviolet radiation [33]. Data for the sample size calculation were obtained directly from the authors. We make the assumption that the erythema based on ultraviolet radiation can be a reasonable substitute for acute radiation dermatitis based on erythema being a part of the RTOG acute radiation morbidity scoring criteria grade 1 and 2 [30]. Based on the study used for the RTOG sample size calculation, we assume that the erythema will be most pronounced 2 weeks after conclusion of radiation therapy. We also make the assumption that melatonin applied twice daily in a 2.5% cream in which it is completely dissolved, will provide an effective dose comparable to the 12.5% used in the study evaluating ultraviolet radiation [17], due to a deposition or depot-effect in the skin [37]. Furthermore, we have been informed by the authors of the previous study utilizing the 12.5% cream that the cream was not homogenous, and contained small granules of undissolved melatonin in both the 2.5%, 5% and 12.5% creams. This suggests that the required dose, to obtain an effect, is in fact smaller than 12.5%. The sample size is calculated based on the a^* -values, where a high a^* -value corresponds to a higher degree of erythema.

Mean (SD) a^* -value for placebo at all time points: 18.4 (3.47)

Mean (SD) a^* -value for 12.5% melatonin cream at all time points: 13.44 (2.36)

Alpha: 5%

Beta: 20%

Sample size needed: Two groups of 8 patients, totaling 16 patients.

The sample size calculation for the QLQ-BR23 breast symptom score is based on a study investigating quality of life following radiation therapy, comparing mastectomy to breast conservation therapy in patients with breast cancer [38]. The data used for the sample size-

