The subjects will be questioned about adverse events once weekly during treatment. An adverse event is defined as any medical event that leads to an unwanted effect in the subject after the administration of the intervention medication, without any necessary connection between the adverse event and the intervention. An adverse reaction is defined as harm or unwanted reaction to a drug, no matter the dosage. We have defined six pre-specified self-reported symptoms (nervousness, confusion, depressed mood, dizziness, headache, or garlic like odor), based on the most commonly reported adverse reactions of melatonin and DMSO available in the literature [41, 50-53]. Patients will also be asked to report additional symptoms of adverse effects, if any. Both adverse reactions and adverse events will be reported in the eCRF.

Serious adverse events (SAE) are defined as any medical effect that result in death, are life-threatening, lead to hospitalization, result in disability or permanent damage, or any other important medical event. All serious adverse events will be registered in EudraCT..

Serious adverse drug reactions (SARs) will be reported annually. Most likely this will not be applicable to this study, as it will last less than a year. In this case, SARs will be reported on conclusion of the study.

Sudden unexpected serious adverse reactions (SUSARs) will be reported immediately to the Danish Medicines Authority and the local ethics committee. Adverse event registration will commence on the first study day and be finalized after the last study day. In case of serious adverse reactions, the sponsor can decide if the study will be terminated. It is the sponsor's responsibility to evaluate if an adverse event is a SUSAR. SUSARs that are lethal or life-threatening will be registered and reported to the Danish Medicines Agency as fast as possible and at the latest 7 days after the sponsor has obtained knowledge of such an adverse event. All other SUSARs will be reported to the Danish Medicines Agency within 15 days. Due to not expecting any serious adverse reactions, all SARs will be considered unexpected and therefore considered SUSARs.

Ethical considerations

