Connective tissue diseases	Patient
Disease and treatment	Source
Tumor type	Pathology report
Tumor size	Surgical report
Location of tumor	Surgical report
Lymph node status	Pathology report
Metastases	Electronic health record
Axillary dissection	Surgical report
Chemotherapy prior to radiation	Electronic health record
Type of chemotherapy	Electronic health record
Radiation dosage	Radiation treatment plan
Hypo-/hyperfractioning of radiation therapy	Radiation treatment plan

¹Central Person Register in Denmark. ²Fitzpatrick scale.

Table 3: Participant timeline

Activity/assessment	Pre-study screening/consent	Pre-study baseline/randomization	First radiation fraction	Study visit week 1	Study visit week 2	Study visit week 3	Study visit week 4	Study visit week 5	Last radiation fraction	Follow-up week 1	Follow-up week 2	Follow-up week 3
Prescreening consent	●											
Screening log	●											
Consent form	●											
Inclusion/exclusion form	●											
Randomization		●										
Demographics questionnaire		●										
Instruction in application of cream		●										
Handover of drug/placebo ^a	●			●			●					
Evaluation of compliance			●	●	●	●	●	●	●			
RTOG score evaluation ^b		●	●	●	●	●	●	●	●	●	●	●
Clinical photography	●	●	●	●	●	●	●	●	●	●	●	●
QLQ-C30 ^c	●	●	●	●	●	●	●	●	●	●	●	●
QLQ-BR23 ^c	●	●	●	●	●	●	●	●	●	●	●	●
Steroid usage evaluation	●	●	●	●	●	●	●	●	●	●	●	●
Monitoring of adverse events	●	●	●	●	●	●	●	●	●	●	●	●
Serious adverse event form ^d												
Conclusion of participation										●		

^a Patients will receive extra trial drug/placebo when required throughout study, therefore, the marked visits might vary from patient to patient depending on compliance. ^b RTOG score = Radiation Therapy Oncology Group cooperative group common toxicity criteria. ^c QLQ-C30 and QLQ-BR23 =European Organization for Research and Treatment of Cancer quality of life questionnaires. ^d Serious Adverse event form will be filled in as needed throughout the trial.

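### Patients who skip follow-up visits have no described route for reporting adverse events from home, and the Harms text and Table 3 disagree on whether patients are questioned after treatment

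*Combined protocol and SAP*

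**What the plan says.** **Home reporting.** The section on drop-outs and patient retention provides for patients who do not want to come to all three follow-up visits. For them, "some of the outcomes can be filled in electronically from home, should the patients wish to do so". The next sentence names the items: "These outcomes are the QLQ-C30 and QLQ-BR23 questionnaires, and steroid usage outcomes". Adverse events, the RTOG score and photographs are not named.

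**Adverse event questioning.** Under Harms, Adverse events: "The subjects will be questioned about adverse events once weekly during treatment". Six self-reported symptoms are asked about (nervousness, confusion, depressed mood, dizziness, headache, garlic-like odor), and patients are also invited to mention anything else.

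**Adverse event registration.** The same subsection says: "Adverse event registration will commence on the first study day and be finalized after the last study day". The last study day is not defined.

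**Visit schedule.** Table 3 has a row "Monitoring of adverse events" with marks in the same pattern as the questionnaire and steroid rows, which the outcome sections say are collected weekly to three weeks after the last fraction. A footnote covers serious events: "Serious Adverse event form will be filled in as needed throughout the trial".

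**The concern.** The plan foresees that some patients will not return after radiotherapy and sets up an electronic route to keep part of their data. That route asks about quality of life and steroid cream but not about harm, although the solicited symptoms are self-reported and need no examination. The sentence on questioning, taken alone, also stops active enquiry when treatment stops.

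At stake is whether the trial asks every patient about harm over the whole period in which it says it registers harm. If the enquiry depends on attendance, the safety record for follow-up depends on who chooses to come. A patient kept away by illness or an admission is one whom the investigator would most want to ask.

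**Working it through.** No sample size or power figure is involved. The check sets the texts side by side and then bounds the size.

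**1. Are patients questioned after the last fraction?**

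| Source | What it implies for follow-up weeks 1 to 3 |
|---|---|
| Harms, sentence on questioning | Weekly questioning belongs to the treatment period |
| Harms, sentence on registration | Registration stays open until after an undefined last study day |
| Table 3, adverse event row | Monitoring appears to run through follow-up week 3 (column alignment is uncertain in the extracted text) |
| Table 3, serious event footnote | Form not tied to any visit |

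The two Harms sentences can be squared in two ways. If the last study day means the last fraction, they agree with each other but not with Table 3. If registration continues but questioning stops, events in follow-up are recorded only when volunteered, which is less than scheduled monitoring at each visit. Neither reading fits all the texts, so they need to be reconciled.

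**2. What happens to a patient who stays at home?** The home list has three items, and adverse events are not among them. The same section collects a phone number and e-mail address, but for retention; it does not say that they are used to ask about harm. The serious event form records an event once someone knows of it. The 7-day limit for reporting fatal or life-threatening unexpected reactions likewise runs from the sponsor's knowledge. No enquiry that would produce that knowledge is described for a patient at home.

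**3. Do health records fill the gap?** The Approvals section seeks permission to use health records and the national patient register. The Confidentiality section ties record access to the information in Table 2, which does not list admissions after enrolment. No search for admissions is described.

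**4. How large is the window?** The Interventions section gives 15 to 30 fractions at 5 per week, which is 15/5 = 3 to 30/5 = 6 weeks. The same sentence states 3 to 5 weeks, so both upper limits are shown. Follow-up is 3 weeks.

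Share of time from first fraction to last visit = 3 / (3 + treatment weeks):
- 3 weeks of treatment: 3/6 = 50%
- 5 weeks of treatment: 3/8 = 37.5%
- 6 weeks of treatment: 3/9 = 33%

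**5. How many patients?** The documents give no rate of skipped visits. Assuming 10% to 25% of about 80 patients:
- 0.10 × 80 = 8 patients; 0.25 × 80 = 20 patients
- Trial-wide share of observation time without enquiry, if each of them misses all three visits: 0.10 × 0.33 = about 3%, to 0.25 × 0.50 = 12.5%

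For a given rate these are upper limits, because the home option also covers a patient who misses only one visit.

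**The case against.** The strongest reply is that the home list is a list of outcomes. The protocol does not class adverse events as outcomes and treats them in a separate Harms section, so their absence from that list does not show that enquiry stops. Attending patients are scheduled for monitoring, serious events have a form that is independent of visits, and contact details are held for everyone. It can be added that "They are scheduled to do this every day from the first to the last fraction of radiation therapy", so follow-up is off treatment, and that patients at home still report breast symptoms and steroid use.

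Part of this stands. A reader might infer that all safety data after treatment are lost. The registration sentence and Table 3 do not support that. A reader might also infer that serious events will not reach the sponsor; the documents show only that no active enquiry is described for patients at home.

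It is tempting to link the gap to the peak of skin injury, because the sample size section says "we assume that the erythema will be most pronounced 2 weeks after conclusion of radiation therapy". For adverse events the link is weak: none of the six solicited symptoms is a skin symptom, and the home questionnaire and steroid items capture part of the skin reaction.

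Nor do the documents show a bias towards finding no harm. If bad skin reactions keep patients away, the plan's own figures (toxicity in 90% on placebo against 41% on melatonin) would make placebo patients absent more often. Their events would then be under-counted, to the disadvantage of melatonin. The Statistical analyses section specifies no between-arm test of adverse events in any case.

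What the reply does not answer is that, followed as written, a patient at home is asked about steroid cream but not about symptoms, other events or admissions. Outcome or not, no remote enquiry about harm is written down. That the cream has stopped does not put follow-up out of scope, since Table 3 appears to schedule monitoring there and the sample size section itself assumes a depot effect in the skin.

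**Conclusion.** The point holds in a limited form and is a cheap improvement. There are two defects: the Harms sentence on questioning does not fit the registration period or Table 3, and no remote adverse event enquiry is described for patients who skip follow-up visits. In those patients non-serious events may be missed, and serious events may come to light only if someone happens to report them. Attending patients are scheduled for monitoring, on the reading that the Table 3 row runs through follow-up.

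The window is 33% to 50% of a patient's time from first fraction to last visit. The 8 to 20 patients, and the 3% to 12.5% of trial-wide observation time, rest wholly on an assumed non-attendance of 10% to 25%. The size and direction of any between-arm bias cannot be determined from the documents.

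A patient who skips follow-up week 2 also has no RTOG score or photograph at a primary time point. That is a separate loss, which the change below does not repair.

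**What to change.** - **Drop-outs and patient retention:** add to the home list the six solicited symptoms, an open field for other symptoms, and a question on any hospital contact or admission since the last report.
- **Harms, Adverse events:** state that patients are questioned weekly during treatment and at follow-up weeks 1, 2 and 3, to match Table 3, and define the last study day.

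The cost is one short form in the existing electronic system, a few sentences of protocol text, and an occasional phone call by the investigator to clarify a self-reported event. No treatment, endpoint or visit changes. Because home reporting is voluntary, the form narrows the gap but does not close it for a patient who neither attends nor replies.
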